Title: A RCT Evaluating Efficacy of Type-I Collagen Skin Substitute vs. Human Amnion Membrane in Treatment of Venous Leg Ulcers

NCT No: NCT06831760

Date: July 8, 2025

Introduction:

Venous leg ulcers (VLUs) are the most common type of chronic lower extremity ulcerations, accounting for 60-80% of all leg ulcers [1]. They affect approximately 0.18% to 1.35% of the general population and impose a substantial economic burden on healthcare systems worldwide [2]. Chronic venous insufficiency leads to sustained hypertension in the venous system, resulting in capillary damage and impaired healing [3]. These ulcers present a significant public health challenge, leading to impaired quality of life, substantial healthcare expenditures, and recurrence rates exceeding 70% [4]. Standard treatments include compression therapy and conventional wound dressings; however, healing rates remain suboptimal, often resulting in prolonged healing times and high recurrence rates [5].

The pathophysiology of venous leg ulcers involves complex interactions between venous hypertension, inflammatory processes, and impaired cellular function within the wound environment. [6] Chronic venous insufficiency leads to increased hydrostatic pressure, capillary leakage, and tissue hypoxia, creating a hostile microenvironment that impedes normal wound healing processes. [7, 8]. The presence of elevated matrix metalloproteinases, chronic inflammation, and bacterial colonization further contributes to delayed healing and wound chronicity. [9]

Wound healing is a complex biological process involving phases of inflammation, proliferation, and remodelling. Traditional wound care often fails to adequately stimulate this cascade in chronic wounds, necessitating the use of advanced biologic dressings. [10]

Recent advances in wound care have led to the development of bioengineered skin substitutes designed to address the underlying molecular and cellular deficits in chronic wounds. [11]

Advanced wound care options such as collagen-based dressings and allografts have been developed to enhance the wound healing microenvironment. Among these, Type-I collagen-based skin substitutes (HPTC) (such as *Helicoll®*) and dehydrated human amnion/chorion membrane (dHACM) have gained prominence [12-15].

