Sixty patients aged 18–80 years with non-infected chronic venous ulcers of more than 4 weeks' duration, measuring between 2 cm² and 25 cm², with adequate arterial inflow (Ankle Brachial Index > 0.8) and willingness to comply with follow-up were included. Exclusion criteria included active infection requiring systemic antibiotics, uncontrolled diabetes, peripheral arterial disease, autoimmune disorders, malignancy, immunosuppression, pregnancy and known allergies to bovine or human-derived products. Patients were randomly allocated into two equal groups using a computer-generated sequence:

- Group A: Treated with High Purity Type-1 collagen-based skin substitute (HPTC) (n=30)
- Group B: Treated with dHACM (n=30)

Intervention: Application protocols followed manufacturer instructions. Wounds were debrided before initial grafting. All patients received standard wound cleaning and compression therapy. In addition:

- Group A received application of HPTC, a high-purity Type-I collagen dressing. The product was sized to cover the entire wound surface with a 1-cm margin and secured with appropriate secondary dressings
- Group B received dHACM graft. The membrane was rehydrated and applied to cover the wound bed completely
- Standard Wound Care for Both Groups - First layer of a non-adherent and porous paraffin gauze followed by Second layer of absorbent gauze pads and then third layer of a soft roll and crepe bandage.

Infection control measures were taken and patient education regarding wound care and leg elevation were given. Repeat application was done if deemed necessary.

Outcome Measures:

Primary Outcome Measure:

- i. Percentage wound area reduction - percentage wound area reduction from week 1 through week 6 plus 1 week follow up measured manually with digital photography

Secondary Outcome Measure:

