- i. **Infiltration of vascularity in the ulcer bed** - Infiltration of vascularity in the ulcer bed on day 5 of application. Vascularity assessment will be done using biopsy on Day 0 of application to be compared with Day 5 after application of Type-I Collagen-based Skin Substitute or Human Amnion/Chorion Membrane. [Time Frame: 6 days]. Histopathological Assessment – Before application and on the 5th day post-application of either HPTC or dHCAM, a 2mm punch biopsy was obtained from the wound edge extending into the wound bed under local anaesthesia (2% lidocaine without epinephrine). Biopsy samples were immediately fixed in 10% neutral buffered formalin for 24 hours, processed through graded alcohols, and embedded in paraffin blocks. Serial sections of 4 μ m thickness were prepared and stained with:
 - i. Hematoxylin and Eosin (H&E) for general morphology
 - ii. Masson's Trichrome for collagen assessment
 - iii. CD31 immunohistochemistry for capillary density evaluation
 - iv. α -SMA immunohistochemistry for fibroblast activity

Histological Parameters Evaluated

1. Vascular Infiltration: Assessed by counting new blood vessels per High Power Field (hpf) **(0-3 scale)**
 - 0: Minimal vascular ingrowth (<5 vessels/hpf)
 - 1: Mild infiltration (5-10 vessels/hpf)
 - 2: Moderate infiltration (11-20 vessels/hpf)
 - 3: Abundant infiltration (>20 vessels/hpf)
2. Neo-epithelialization: Measured as epithelial migration distance from wound edge **(0-3 scale)**
 - 0: No epithelial migration
 - 1: Minimal migration (<25% wound coverage)
 - 2: Moderate migration (25-75% coverage)
 - 3: Extensive migration (>75% coverage)

3. Fibroblast Activity: Quantified by counting α -SMA positive fibroblasts per HPF and assessment of fibroblast morphology (**0-3 scale**)
 - 0: Sparse, inactive fibroblasts
 - 1: Moderate cellularity, minimal matrix production
 - 2: High cellularity, active-matrix synthesis
 - 3: Very high activity with extensive matrix deposition
4. Capillary Density: Evaluated using CD31 staining, counted as vessels per mm^2 of tissue
5. Inflammatory Response: Graded semi-quantitatively (**0-3 scale**)
 - 0: Minimal inflammatory infiltrate
 - 1: Mild chronic inflammation
 - 2: Moderate mixed inflammation
 - 3: Severe acute inflammation
6. Collagen Deposition: Assessed using Masson's Trichrome staining (**0-3 scale**)
 - 0: Minimal collagen matrix
 - 1: Loose, immature collagen
 - 2: Moderate organized collagen
 - 3: Dense, mature collagen architecture

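### The Inflammatory Response scale ties each severity above minimal to a different inflammation type, so moderate or severe chronic inflammation and other pairings have no matching grade

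*Protocol*

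**What the plan says.** Under the first secondary outcome, the protocol's list of histological parameters gives item 5 as "Inflammatory Response: Graded semi-quantitatively", on a 0-3 range. The four grades are:

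- "0: Minimal inflammatory infiltrate"
- "1: Mild chronic inflammation"
- "2: Moderate mixed inflammation"
- "3: Severe acute inflammation"

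Biopsies are taken before application and on day 5. Two pathologists read every slide independently, without knowledge of the arm, and their agreement is summarised by Cohen's kappa. No rule is given for a slide that fits none of the grades.

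The SAP (Data Analysis) does not define the scale further. It plans t-tests for continuous variables, chi-square tests for categorical ones, and Cohen's d for the main histology parameters, which it does not list.

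On the kind of inflammation to expect, the Introduction states: "The presence of elevated matrix metalloproteinases, chronic inflammation, and bacterial colonization further contributes to delayed healing and wound chronicity". The eligibility text enrols "non-infected chronic venous ulcers of more than 4 weeks' duration".

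**The concern.** The severity words rise in order from grade 0 to grade 3, so the score reads naturally as an amount of inflammation. But the type changes at each step as well, from chronic to mixed to acute. One number therefore carries two quantities, and it is defined only where they move together.

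The trial enrols chronic, non-infected ulcers, and the only grade for purely chronic inflammation is the mild one. A pathologist who sees more than mild chronic inflammation has to choose which half of the definition to honour, possibly already at baseline.

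At stake is what a difference in this score means. A change from Day 0 to Day 5, or a gap between the arms, could be a change in amount, a change in type, or the result of how off-scale slides were coded.

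**Working it through.** The plan gives no figure for this parameter, so there is none to reproduce. The check is a count of pairings, followed by what happens to a slide that fits none of them.

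**Inputs.** Three severities above minimal (mild, moderate, severe) and three types (chronic, mixed, acute), all taken from the wording of grades 1 to 3. Grade 0 names no type and causes no difficulty.

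**Step 1: cross severity with type.**

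| | chronic | mixed | acute |
|---|---|---|---|
| mild | 1 | none | none |
| moderate | none | 2 | none |
| severe | none | none | 3 |

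3 severities × 3 types = 9 pairings. Defined: 3. Undefined: 9 − 3 = 6, namely mild mixed, mild acute, moderate chronic, moderate acute, severe chronic and severe mixed.

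**Step 2: grade one undefined slide.** Take severe chronic inflammation. Matching on type gives 1, matching on severity gives 3, and a compromise gives 2. The admissible answers span the whole range above minimal.

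**Step 3: follow hypothetical changes from Day 0 to Day 5.**

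- Moderate chronic to moderate acute (same amount, different type). Matched on type: 1 to 3, a change of +2. Matched on severity: 2 to 2, a change of 0.
- Severe chronic to moderate mixed (amount falls). Matched on type: 1 to 2, a change of +1. Matched on severity: 3 to 2, a change of −1. The sign depends on the convention.

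These cases show what the scale permits. They do not estimate how often it happens.

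**Step 4: look for a safeguard.** Blinding to arm means that knowledge of treatment cannot steer the choice. Kappa would show two readers who resolve such slides differently, but it does not say which grade is right. If both use the same convention, kappa can be high while the score still mixes amount and type. None of the SAP's tests or effect sizes can separate the two once they are merged in one grade.

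**The case against.** The best reply is that the scale may be meant as a composite, running from quiescent tissue to florid acute inflammation, in which case a move from chronic to acute should score higher. Composite grading is also the protocol's habit: its fibroblast item joins cellularity with matrix production, and its collagen item joins density with maturity. This reply has some force, since the protocol never says that the scale measures amount alone. But it does not state the composite reading either, and even on that reading the six other pairings need a rule.

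A second reply is that the severity words are ordered, so a pathologist can simply grade on severity. That is workable, and it is close to the remedy below, but it is not written down.

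A third is that the Day 0 to Day 5 comparison is spelled out only for vascularity, and that inflammation may not be among the parameters given a Cohen's d. This stands, and it limits how much rests on the score.

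Two stronger readings are tempting. A reader might infer from the Introduction that severe chronic inflammation is likely, or that the undefined patterns are common. The Introduction names chronic inflammation without giving a severity, mild chronic inflammation fits it equally well and has a grade, and no frequencies appear anywhere. A reader might also infer that the score is uninterpretable. That goes too far: slides that match a grade are scored without difficulty, and blinded double reading protects the comparison of arms from deliberate or unconscious steering.

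**Conclusion.** The point holds as a defect in the definition of one scale. Each severity above minimal is tied to a different type, six of nine pairings have no grade, and the two above-mild purely chronic patterns are among the six. A difference in grade can therefore reflect type rather than amount.

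The practical size is unknown. The six-of-nine count treats all pairings alike and says nothing about misgrading rates, kappa or any result. The conclusion rests on the written grades and on the absence of a coding rule in either document; it assumes nothing about how often off-scale slides arise.

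The reach is small: one of six histological parameters under a secondary outcome, with no bearing on wound-area reduction as the primary outcome or on the sample size. Rating: cheap improvement.

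**What to change.** Grade severity alone as the analysed score (0 minimal, 1 mild, 2 moderate, 3 severe). On the same slide read, record type (chronic, mixed or acute) as a separate descriptive field. Every pairing can then be recorded, and a change in type no longer moves the score.

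If slides are still to be read, the cost is a reworded scale and one extra field, with the same slides and the same pathologists. Both documents are largely in the past tense, so reading may be complete. In that case the cost is a blinded re-read, by both pathologists, of slides from both time points, if they were retained; the documents do not say whether they were.

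If a re-read is not possible, report the convention used for slides outside the three defined pairings, and do not interpret the grade as amount of inflammation alone.

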All histological assessments were performed by two independent pathologists blinded to treatment allocation. Inter-observer agreement was assessed using Cohen's kappa coefficient.

- ii. Time to achieve complete wound closure - the time to achieve complete wound closure (defined as 100% epithelialization with no drainage) of the target ulcer by the end of 6 weeks [Time Frame: 6 weeks]
- iii. Proportion of subjects to obtain complete closure - the proportion of subjects that obtain complete closure over the 6-week treatment period [Time Frame: 6 Weeks]
- iv. Mean number of repeated application - mean number of repeated applications of the Advanced Skin Substitute & Human Amnion/Chorion Membrane used to obtain wound closure [Time Frame: 6 Weeks]
- v. Incidence of adverse events - incidence of adverse events related to the intervention (e.g., infection, allergic reactions) [Time Frame: 6 Weeks]

Other Pre-specified Outcome Measures:

- i. Change in Pain - change in pain measured by a Visual Analog Scale with score range from 0 to 10, wherein 0="no pain" to 10="severe pain" [Time Frame: 7 weeks including 1-week follow-up]. Pain scores were assessed weekly.
- ii. Change in quality of life - change in quality of life assessed using the Wound-QoL questionnaire measured as 'not at all', 'a little', 'moderately', 'quite a lot' and 'very much' for 17 questions [Time Frame: 7 weeks including 1-week follow-up]
- iii. Healed Wound appearance assessment using Manchester Scar Scale - the resultant new skin is assessed and documented at each visit using the Manchester Scar Scale assessing colour, finish, contour, distortion & texture with values given from 1 to 4 wherein 1 denotes excellent and 4 means poor [Time Frame: 7 weeks including 1-week follow-up]

Data Collection and Monitoring

- a. Baseline data: Demographics, medical history, ulcer characteristics.
- b. Weekly follow-ups: Wound measurements (photographic documentation), assess healing progress, pain scores, record adverse events and patient-reported outcomes.
- c. Histopathological specimens were obtained at baseline and day 5 for vascularity assessment.
- d. End-of-Study Visit (Week 6): final wound assessment, collect patient feedback on treatment experience, quality of life and scar assessment.
- e. Data entry and monitoring was managed using an electronic data capture system.

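### Cohen's kappa, with no weighting stated, is the only agreement measure named for the histology: it does not suit the numeric capillary density, and its default form ignores how far apart the 0-3 grades are

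*Protocol*

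**What the plan says.** The protocol's first secondary outcome rests on punch biopsies taken before application and on day 5. Under Histological Parameters Evaluated it lists six parameters. Vascular infiltration, neo-epithelialization, fibroblast activity, inflammatory response and collagen deposition are each graded 0 to 3. The remaining one is numeric, and no cut-points are given for it: "Capillary Density: Evaluated using CD31 staining, counted as vessels per mm^2 of tissue".

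Right after that list the protocol says: "All histological assessments were performed by two independent pathologists blinded to treatment allocation". The next sentence is the whole plan for reliability: "Inter-observer agreement was assessed using Cohen's kappa coefficient". It does not say which parameters it covers, whether the kappa is weighted, or what happens if agreement is poor. No ICC, limits of agreement or weighted kappa appears in either document. The Data Analysis section of the SAP mentions histology only for Cohen's d effect sizes.

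**The concern.** Kappa compares the observed share of identical classifications with the share expected by chance, so it needs categories. Capillary density has none. If each distinct value is treated as a category, two readers who differ by one vessel per mm² count as disagreeing completely, and a reproducible measurement can look unreliable. If density is categorised first, the result depends on cut-points that the plan does not give.

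The 0-3 grades are categories, but ordered ones. In its default, unweighted form kappa gives a 0-versus-3 disagreement the same penalty as 1-versus-2. This matters where a grade is cut from a count: under the protocol's scale for vascular infiltration, 10 vessels per high-power field is grade 1 and 11 is grade 2, so one vessel can cost as much as a disagreement across the whole scale.

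What is at stake is how far a reader can trust the histology. Blinded double reading with an agreement statistic is the plan's own check on those readings. An unsuitable statistic could discredit sound density data or hide gross disagreement on the grades.

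**Working it through.** The documents give no kappa value, target or reliability sample size, so there is no figure to reproduce. The means, SDs and agreement tables below are assumptions chosen to show size.

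**1. Capillary density**

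Assume readings with mean 60 and total SD 20 vessels per mm², two readers without bias, and values rounded to whole numbers. The SD of the difference between readers on one specimen is 20 × √(2(1 − ICC)). The chance that two rounded values match is about 1/(SD of difference × √(2π)). For two unrelated specimens the SD of the difference is 20 × √2 = 28.28, so the expected chance agreement is Pe ≈ 1/(28.28 × 2.507) = 0.0141. Kappa = (Po − Pe)/(1 − Pe), where Po is the observed agreement.

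| ICC | SD of difference | Po | Kappa |
|---|---|---|---|
| 0.90 | 8.94 | 0.0446 | (0.0446 − 0.0141)/0.9859 = 0.03 |
| 0.95 | 6.32 | 0.0631 | (0.0631 − 0.0141)/0.9859 = 0.05 |
| 0.99 | 2.83 | 0.1410 | (0.1410 − 0.0141)/0.9859 = 0.13 |

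Simulation of reader pairs gives the same values to two decimals.

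A second set of assumptions used 120 specimens (60 patients × 2 biopsies), means of 50 to 200, a between-specimen SD of 30% of the mean, and reader error of 5% to 10%. It gave kappa of 0.01 to 0.11 where the ICC was 0.89 to 0.97. The exact value depends on the assumptions; the gap between kappa and ICC appears under all of them.

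**2. The 0-3 grades**

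Assume that both readers use each grade for 25% of specimens and agree exactly on 70%.

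- Unweighted: Pe = 4 × 0.25² = 0.25, so kappa = (0.70 − 0.25)/(1 − 0.25) = 0.60, wherever the other 30% fall.
- Weighted: kappa = 1 − (mean observed penalty)/(mean penalty expected by chance). With uniform margins the expected linear penalty, |i − j|/3, is 1.25/3 = 0.4167. The expected quadratic penalty, (i − j)²/9, is 2.5/9 = 0.2778.

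| Where the 30% fall | Unweighted | Linear | Quadratic |
|---|---|---|---|
| All one grade apart | 0.60 | 1 − (0.30/3)/0.4167 = 0.76 | 1 − (0.30/9)/0.2778 = 0.88 |
| All 0 versus 3 | 0.60 | 1 − 0.30/0.4167 = 0.28 | 1 − 0.30/0.2778 = −0.08 |

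Both tables can be built with uniform margins. In the first, the diagonal is 0.20, 0.15, 0.15, 0.20 with 0.05 in each adjacent cell. In the second, the diagonal is 0.10, 0.25, 0.25, 0.10 with 0.15 in each of the two corner cells.

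So an unweighted kappa of 0.60 fits both readers who nearly always come within one grade and readers who contradict each other in 30% of specimens.

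**The case against.** The strongest reply is that the protocol does not say what is held against it. The word for all in the first sentence describes who read the slides; the kappa sentence names no parameters. Kappa may have been meant only for the five graded parameters, which would leave density with no agreement measure rather than an invalid one. This stands as a caution. Coverage of every parameter is the natural reading, because no other measure is named and density is not exempted, but it is an inference. Either way density lacks a suitable measure.

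Second, a reader might infer that the plan fixes an unweighted kappa. It does not: weighting is not stated. Cohen's kappa without qualification normally means the unweighted form, but the supportable statement is that the weights are unspecified.

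Third, a reader might conclude that a kappa on the grades would be wrong. That goes too far. Unweighted kappa is a legitimate measure of exact agreement; it is less informative on an ordered scale. The choice of weights is also open to argument. The inflammatory response scale runs from mild chronic through moderate mixed to severe acute inflammation, so it mixes severity with type, and neither equal nor squared spacing is obviously right there.

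Fourth, a reader might infer that a near-zero reliability was, or will be, reported for density. Nothing in the documents says that kappa was computed on raw densities. The figures above show what would happen if it were.

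Last, the consequence is small. No threshold, adjudication rule or test in either document depends on the agreement statistic. This stands in full and sets the weight of the point.

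**Conclusion.** The point holds as a minor one. The plan names Cohen's kappa, without weights, as its only agreement measure for histology that includes a numeric parameter.

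- For capillary density, kappa is not a valid agreement measure. Under the stated assumptions it would be about 0.03 to 0.13 where the ICC is 0.90 to 0.99.
- For the five grades, the default form is valid for exact agreement but blind to distance. The same 0.60 can go with a quadratic-weighted value of 0.88 or of −0.08.

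The first conclusion rests on the natural reading that the kappa sentence covers all six parameters; if it does not, density has no planned measure at all. The second rests on the default meaning of the term. All the numerical values are illustrations, since the documents give no densities, margins or agreement rates.

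The effect is confined to the reported reliability of secondary histology. The documents do not support extending it to the primary outcome of wound area reduction, to the sample size of 30 per group, or to the between-group comparisons.

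**What to change.** Replace the single sentence on agreement, and carry the replacement into the SAP, so that agreement is reported separately for each parameter:

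- **Capillary density:** a two-way, absolute-agreement ICC with Bland-Altman limits of agreement. Do the same for raw vessel and fibroblast counts if these were recorded.
- **The five 0-3 grades:** a weighted kappa with the weights (linear or quadratic) named in advance, alongside the unweighted value. If a weighted kappa was always intended, say so and name the weights.

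The cost is a short change of wording and a minor extra analysis, with no new biopsies or patients. It does need each pathologist's separate readings to have been kept. The documents describe two independent readers but do not say that both sets of readings, or the raw counts behind the grades, were retained; this should be confirmed first.

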HPTC is a high purity Type-I collagen matrix derived from bovine tendon and processed to preserve native triple-helix structure, providing a biocompatible scaffold for cellular ingrowth and promote angiogenesis [16]. dHACM comprises preserved amniotic tissue layers, rich in cytokines and growth factors, and extracellular matrix components that theoretically promote wound healing through regenerative mechanisms. Clinical studies have demonstrated the efficacy of dHACM in various chronic wound types [17].

Recent systematic reviews indicate that bioengineered skin substitutes may improve healing outcomes in venous leg ulcers, with healing probabilities ranging from 0.11 to 0.65 over variable time periods. Clinical trials with dHACM have demonstrated healing rates of 75% at 12 weeks in venous leg ulcers [18-20].

Prior studies in diabetic foot ulcers have reported promising results using HPTC compared to dHACM [21, 22]. While numerous studies have evaluated treatments individually, direct comparative studies evaluating their relative efficacy in venous leg ulcer management is null. The present study aims to bridge this gap by conducting a randomized, controlled clinical trial comparing the efficacy of HPTC and dHACM in terms of healing efficacy and patient-reported outcomes.

Materials and Methods:

This single-centre, prospective, randomized, open label, single-blinded, controlled, parallel-group clinical trial was conducted at a tertiary care centre over a 6-month period. The study protocol was reviewed and approved by the Adichunchanagiri Institute of Medical Sciences Institutional Ethics Committee with approval number AIMS/IEC/004/2025 and conducted in accordance with the Declaration of Helsinki. All participants provided written informed consent before enrolment. Additionally, all study products used in this study were manufactured, handled, and stored in accordance with applicable Good Manufacturing Practices. The study was registered in Clinical Trials.gov with identity number NCT06831760. Confidentiality was maintained with all patient records.

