Title: A RCT Evaluating Efficacy of Type-I Collagen Skin Substitute vs. Human Amnion Membrane in Treatment of Venous Leg Ulcers

NCT No: NCT06831760

Date: July 8, 2025

Study Aims

This randomized, controlled clinical trial aimed to compare clinical efficacy, healing outcomes, of High Purity Type-I Collagen Skin Substitute (HPTC) vs. Dehydrated Human Amnion / Chorion Membrane (dHACM) in the treatment of venous leg ulcers.

Sample Size Calculation

Standard Two-Sample Comparison of Proportions (e.g., wound closure rate)

Assuming:

- $\alpha = 0.05$ (5%)
- **Power** = 0.80 (80%)
- **Proportion of success in control (p_1)** = 0.60 (typical healing rate for dHACM)
- **Proportion of success in treatment (p_2)** = 0.90 (expected improvement with Type-I collagen)

We use the formula for comparing two proportions:

$$n = (p_1 - p_2)^2 (Z\alpha/2 + Z\beta)^2 / [p_1(1 - p_1) + p_2(1 - p_2)]$$

Where:

- $Z\alpha/2 = 1.96$ for $\alpha = 0.05$
- $Z\beta = 0.84$ for 80% power

$$n = (1.96 + 0.84)^2 \cdot [0.6(0.4) + 0.9(0.1)] / (0.9 - 0.6)^2 = 7.84 \cdot [0.24 + 0.09] / 0.09 = 7.84 \cdot 0.33 / 0.09 = 2.59 / 0.09 \approx 28.8$$

We use the formula for comparing two proportions:

$$n = \frac{(Z_{\alpha/2} + Z_{\beta})^2 \cdot [p_1(1 - p_1) + p_2(1 - p_2)]}{(p_1 - p_2)^2}$$

Where:

- $Z_{\alpha/2} = 1.96$ for $\alpha = 0.05$
- $Z_{\beta} = 0.84$ for 80% power

$$n = \frac{(1.96 + 0.84)^2 \cdot [0.6(0.4) + 0.9(0.1)]}{(0.9 - 0.6)^2} = \frac{7.84 \cdot [0.24 + 0.09]}{0.09} = \frac{7.84 \cdot 0.33}{0.09} = \frac{2.59}{0.09} \approx 28.8$$

~29 participants per group - 30 per group is statistically adequate to detect a difference from 60% to 90% healing rate with 80% power.

Randomization and Blinding: Patients were randomized 1:1 to the HPTC or dHCAM group using a computer-generated randomization sequence. Open-label design (patients and clinicians were aware of treatment allocation). Outcome assessors and statisticians were blinded.

Data Collection and Monitoring

- a. Baseline data: Demographics, medical history, ulcer characteristics.
- b. Weekly follow-ups: Wound measurements (photographic documentation), assess healing progress, pain scores, record adverse events and patient-reported outcomes.
- c. Histopathological specimens were obtained at baseline and day 5 for vascularity assessment.
- d. End-of-Study Visit (Week 6): final wound assessment, collect patient feedback on treatment experience, quality of life and scar assessment.

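### The only safety outcome counts intervention-related adverse events in an open-label trial, with no stated (or stated-blind) judge of relatedness; an all-event table by arm should be added

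*Protocol*

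**What the plan says.** Protocol, Secondary Outcome Measure v, defines safety as the "incidence of adverse events related to the intervention (e.g., infection, allergic reactions) [Time Frame: 6 Weeks". No other outcome in either document covers adverse events. The SAP's Data Analysis paragraph does not mention them, so they fall under its general rule for categorical variables, a chi-square test at p<0.05.

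On collection, item b of Data Collection and Monitoring (the same in both documents) says that weekly visits "record adverse events and patient-reported outcomes". It sets no relatedness limit, but it does not say that every event is captured.

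On blinding, the Protocol calls the trial a "randomized, open label, single-blinded, controlled, parallel-group clinical trial". The SAP, Randomization and Blinding, states "Open-label design (patients and clinicians were aware of treatment allocation" and then "Outcome assessors and statisticians were blinded". The Protocol separately says that two pathologists read the histology blind. It makes no comparable statement about adverse events.

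On timing, the primary outcome is "percentage wound area reduction from week 1 through week 6 plus 1 week follow up", and pain, quality of life and scar appearance each carry "Time Frame: 7 weeks including 1-week follow-up". Item d of Data Collection and Monitoring nevertheless places the End-of-Study Visit, with the final wound assessment, at Week 6.

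**The concern.** Randomisation protects a comparison of all events between the arms. It does not protect a comparison of events selected after allocation by a judgement that may be made with knowledge of the product. If relatedness is decided more readily in one arm than in the other, the outcome can show a difference where none exists or hide one that does.

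The risk is practical here because infection, the outcome's first example, has several plausible causes. The ulcers are chronic, are debrided before the first graft, and are punch-biopsied at baseline and again on day 5. An infection could be put down to the ulcer, the debridement, the biopsy or the product, and the documents give no criteria for choosing.

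The time window is a smaller matter. The safety outcome has a 6-week frame, while four other outcomes have a 7-week frame. Any adverse event seen in a seventh week would fall outside the safety outcome.

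**Working it through.** **The plan's own figure.** The documents give no number for safety. Their one calculation, for wound closure, reproduces: (1.96 + 0.84)² × [0.6 × 0.4 + 0.9 × 0.1] / 0.3² = 7.84 × 0.33 / 0.09 = 28.75, so 29 per group, set at 30. Nothing below depends on it beyond the 30 per arm.

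**Who decides relatedness.** Three statements have to be set side by side:
- The outcome counts only related events (Protocol, secondary outcome v).
- Patients and clinicians are unblinded; outcome assessors are blinded (SAP, Randomization and Blinding).
- Events are recorded at weekly visits (Data Collection and Monitoring, item b), with no mention of a causality assessment, criteria or a named judge.

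The outcome cannot be produced without a relatedness decision, and the documents do not say whether that decision is blinded.

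**Effect of attribution.** Inputs: 30 per arm (documents); the true event rate R, the same in both arms, and the shares a and b of events called related in the two arms (all assumed). The reported rates are R × a and R × b, and the apparent risk ratio is a/b.

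| R (assumed) | 50% vs 50% | 70% vs 50% | 80% vs 40% |
|---|---|---|---|
| 10% | 5% vs 5% | 7% vs 5% | 8% vs 4% |
| 20% | 10% vs 10% | 14% vs 10% | 16% vs 8% |
| 30% | 15% vs 15% | 21% vs 15% | 24% vs 12% |
| Apparent risk ratio | 1.0 | 1.4 | 2.0 |

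At R = 20%, 6 of 30 patients per arm truly have an event. The expected counts reported are 3 vs 3, 4.2 vs 3, or 4.8 vs 2.4. Either arm could be the one with the higher share.

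**Would it reach significance?** Rounding the most extreme 20% case to 5 vs 2 of 30, the uncorrected chi-square is 60 × (5 × 28 − 2 × 25)² / (30 × 30 × 7 × 53) = 1.46, p = 0.23; Fisher's exact p = 0.42. The distortion would be in the reported percentages, not in a significant test. The absence of events would also say little: 0 of 30 is compatible with a true rate up to 1 − 0.05^(1/30) = 9.5% (one-sided 95% bound).

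**The window.** If follow-up does run to week 7, the safety frame leaves out 1/7 = 14.3% of the weeks. That is a share of time, not of events. Under an assumed constant hazard, the 6-week risk is 1 − (1 − R₇)^(6/7), where R₇ is the 7-week risk:

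| 7-week risk (assumed) | 6-week risk | Patients missed, of 60 |
|---|---|---|
| 5% | 4.3% | 0.4 |
| 10% | 8.6% | 0.8 |
| 20% | 17.4% | 1.6 |
| 30% | 26.3% | 2.2 |

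**The case against.** The strongest reply is that the SAP does state that outcome assessors were blinded, and adverse event incidence is a listed outcome, so that sentence may cover it. A reader might infer from the open-label design that unblinded clinicians decided relatedness. The documents do not support that; they are silent. What stands is the silence: the blinding sentence does not assign causality to the assessors.

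Second, no case-by-case causality review is described. Infection and allergic reaction could simply be the expected local events to be counted. That reading is possible, but the wording still restricts the outcome to related events, and neither document says that every infection counts.

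Third, a reader might infer that all adverse events are already in the database. The text says only that adverse events are recorded. If relatedness was applied at collection, an all-event table could not be built retrospectively. This objection stands and limits what the fix can promise.

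Fourth, a reader might infer that patients were certainly seen at week 7 and that a week of events is discarded. The End-of-Study Visit is at Week 6, which conflicts with the 7-week frames, so a week-7 contact cannot be taken as fact. The 6-week safety frame also matches the treatment period and secondary outcomes ii to iv. The window is therefore an inconsistency to reconcile, not a demonstrated loss of data.

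Finally, both documents are written in the past tense, so replacing a stated outcome could be a post hoc change. That favours adding a table over redefining the outcome.

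**Conclusion.** The point holds in a limited form. The only safety outcome is restricted to related events, patients and clinicians were unblinded, and the documents do not say who decides relatedness or whether that person is blinded. Differential attribution could therefore shift the between-arm comparison with no true difference in events.

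The size depends wholly on assumed values. With attribution shares between 50% vs 50% and 80% vs 40%, the apparent risk ratio runs from 1.0 to 2.0. A reader might take the doubling as the expected effect, but it is the far end of the range shown, and no data in the documents point to it. Nor do the documents show that biased attribution occurred.

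The week-7 question is secondary and rests on a conflict within the documents. The primary analysis, sample size and power are untouched. This is a cheap improvement.

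**What to change.** In the SAP, keep secondary outcome v as stated and add beside it, by arm:
- the number and percentage of patients with any recorded adverse event, regardless of relatedness;
- infection and allergic reaction as separate rows, also regardless of relatedness;
- related events as a further row, with a statement of who decided relatedness and whether that person was blinded.

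Report events through the last actual contact. Reconcile the Week 6 End-of-Study Visit with the 7-week time frames of the primary, pain, quality-of-life and scar outcomes. If adverse events were not captured at week 7, or if only related events were recorded, say so in the report.

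The cost is a short SAP addition and a few table rows. The reported event percentages will be higher, and the new table should be labelled as an addition to the stated outcome. If only related events were collected, the all-event rows cannot be produced and that statement takes their place.
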